19.2 Planned recruitment rate

This single site study will be performed at the Royal London Hospital Major Trauma Centre, Barts Health NHS Trust. The hospital sees approximately 2200 trauma patients a year, of which 550 are severely injured. In 2014 the number of trauma patients who activated the major haemorrhage protocol (either pre-hospital or in the emergency department) was 143 over the 12-month period.

Our department has previous experience with randomizing patients with major haemorrhage into interventional trials. The Cryostat study (Curry *et al.* 2015), conducted in 2012-13, successfully randomized 31.8% of potentially eligible adult trauma patients with major haemorrhage over a 15-month period. 68% of all major haemorrhage protocol activations were considered eligible for recruitment in that study. Of the randomized patients, only one patient (0.02%) withdrew consent.

Recruitment for the Cryostat study was between the hours of 8 am and 8-10pm, and the reason for non-enrolment of 69% of eligible patients was they fell outside of recruitment hours. For TOP-ART, recruitment hours will be extended to recruit eligible patients 24 hours a day, 7 days a week. Based on the Cryostat study and the extended recruitment hours, it is anticipated that 24 months will provide sufficient duration to recruit the planned number of participants, taking into consideration potential screen failures and participant withdrawals, and the duration of funding.

At present there are no other ongoing interventional trials competing for the same cohort of patients within or outside the department. In the event another competing study is commenced

within the same department, priority will be given to the TOP-ART trial to ensure that recruitment is not compromised. The clinical trial coordinator and lead clinical fellow are responsible for tracking and driving recruitment rates.

19.3 Statistical analysis plan (SAP)

Full details of planned statistical summaries and analyses will be described in a separate Statistical Analysis Plan. Any deviations from the statistical analysis plan will be fully documented in the clinical study report, with the reasons for doing so. A brief summary of the SAP is provided below (see also Sections 19.4-19.13).

An interim analysis will be performed after recruitment of the first 52 patients. The analysis will be limited to an analysis of safety data between the two groups. Provided there are no issues regarding safety or toxicity, the study will be continued with an increased dose in the intervention arm.

The final analysis will be performed according to standard trial best-practice criteria. All data analysis will be performed before the breaking of the randomization code. Standard tests of two-group comparison will be used throughout. One- and two-way ANOVA will be used to analyse time-dependent (pKa) data. Safety data will be re-analysed with the final cohort as outlined for the interim analysis (see Section 19.9).

19.4 Summary of baseline data and flow of patients

Demographic information and baseline characteristics will be summarised for each treatment group by type of variable; categorical data (including gender) using counts and percentages, and continuous variables (including age, ISS, blood products and fluids in the first 24 hours) by means, standard deviations, medians, minima, maxima, and numbers of subjects, as appropriate. Baseline comparability of demographic and baseline characteristics for the three treatment groups will be performed.

A CONSORT flow diagram will be provided to illustrate how the study population was recruited and handled during the course of the study. The number (%) of subjects who withdraw from the study and their reasons for withdrawal will be displayed by treatment group.

19.5 Primary outcome analysis

The primary endpoint is the SOFA score at 48 hours; placebo and treatment groups will be analysed using standard tests of two-group comparison depending on data normality. Intention to treat and per protocol analyses will be performed. The main analysis will be the per protocol analysis. There are no pre-determined subgroup analyses.

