Subjects who do not complete the primary outcome end-point at 48-hours (e.g. due to death or discharge) will be replaced. Variables will be evaluated at different time points from screening through day 28 as per the schedule of events.

Adverse events (AEs) and serious adverse events (SAEs) will be reviewed by the trauma research fellow (who is a clinician) on a daily basis from the point of dosing throughout the 28-day subject participation in the trial. Please see Section 17 for further details.

The following will be determined at various points throughout the trial SOFA score, renal injury, lung injury, infection rate, the number of mechanical ventilation days, RRT days, vasopressor days, CTCOFR score, ACCU length of stay and the hospital length of stay.

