13.9 Withdrawal criteria

Every reasonable effort will be made to maintain protocol compliance and to retain patient participation in the study consistent with the provisions of informed consent and good clinical practice. The following are potential reasons why a patient may be withdrawn from the study:

- 1. Withdrawal of consent: the patient, the patient's authorised representative, independent physician, or designated individual who had provided initial consent to enter the study may withdraw consent at any time throughout the duration of the trial, without prejudice to future medical care and treatment.
- 2. Retrospective exclusion: If a patient is deemed to not meet one or more of the inclusion/exclusion criteria in retrospect they will be withdrawn from the study.
- 3. Major protocol deviation from the study design by the subject, observed or suspected by the investigator.
- 4. Adverse event.
- 5. Administrative: the sponsor or monitoring committees decide to terminate or discontinue the study.
- 6. The subject's health would be jeopardised by continued participation and is withdrawn at the discretion of the investigator.

Data Collection And Follow-Up For Withdrawn Subjects

If a patient is withdrawn from the study before receiving IMP but after randomisation, any ongoing SAE experienced by the patient, which are not injury- or standard-treatment related, will be followed to resolution but no other safety or efficacy assessments will be conducted.

Patients who withdraw from the study after receiving IMP should be followed for safety by conducting safety assessments through to the end of day 28. If a patient who withdraws has develops an SAE during the monitoring period, every effort must be made to follow such events until satisfactory resolution is obtained or until further follow-up is no longer warranted.

Any samples obtained from withdrawn participants will be discarded in accordance with the Bart's Health NHS Trust standard procedures.

Replacement Of Subjects

Subjects who do not complete the primary outcome end-point at 48-hours (e.g. due to death or discharge) will be replaced. Subjects who withdraw from the study at any time point will also be replaced. Withdrawn participants will not be permitted to re-enter the study.

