19.10 Subject population

The analysis populations will be defined as follows:

Intent-to-Treat (ITT) Population

The ITT population is defined as all patients randomised according to their treatment allocation irrespective of whether they received that treatment or not.

Per Protocol (PP) Population

Version 2.0 TOP-ART

The PP population is defined as all patients randomised and treated according to the protocol i.e. based on treatment that patients actually received. The primary efficacy analysis will be performed on this study population.

Safety Population

The safety population is defined as all patients randomised who received any partial dose of IMP and will be analysed based on treatment that patients actually received.

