19.11 Procedure(s) to account for missing or spurious data

The study team will follow participants daily in order to maximise capture of follow-up data. Missing outcome data will be imputed where appropriate. Reasons for missing data will be recorded on the CRF during data capture where possible (e.g. observation not performed, sample not taken).

19.12 Other statistical considerations.

Any deviations from the original statistical plan will be reported in the clinical study report with reasons for doing so. Participants who withdraw from the study will be replaced. Evaluable patients are defined as those who meet study inclusion and exclusion criteria, provide consent for participation, are randomised to either treatment or comparator group and treated according to protocol, and reach the primary endpoint (SOFA score at 48 hours). Evaluable patients will analysed in the 'per protocol' analysis for comparison against the intention-to-treat analysis.

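### The primary comparison is limited to patients who reach the 48-hour SOFA, and early deaths and discharges are replaced, so it is conditioned on outcomes that treatment can change

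*Protocol*

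**What the plan says.** Section 19.5 plans two analyses, "Intention to treat and per protocol analyses will be performed", and ranks them: "The main analysis will be the per protocol analysis". Section 19.10 defines the per-protocol set as patients randomised and treated according to protocol, grouped "based on treatment that patients actually received. The primary efficacy analysis will be performed on this study population".

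Section 19.12 adds a condition that 19.10 lacks. Evaluable patients must also be eligible, consented, treated per protocol "and reach the primary endpoint (SOFA score at 48 hours", and these evaluable patients form the per-protocol analysis, to be set against intention to treat (ITT).

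Section 11.6, repeated in 13.9, reads: "Subjects who do not complete the primary outcome end-point at 48-hours (e.g. due to death or discharge) will be replaced". Sections 13.9 and 19.12 also replace withdrawals.

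Section 13.9 lists retrospective ineligibility, major deviation and adverse event among the reasons for withdrawal. For the first it is firm: "If a patient is deemed to not meet one or more of the inclusion/exclusion criteria in retrospect they will be withdrawn from the study". For patients withdrawn after randomisation but before dosing, apart from following certain ongoing serious adverse events, "no other safety or efficacy assessments will be conducted". Patients withdrawn after dosing are followed for safety to day 28.

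Section 19.11 says missing outcomes are imputed where appropriate. It names no value or rank for death or discharge before 48 hours.

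**The concern.** Randomisation makes the arms comparable at entry. It does not make comparable the subsets that are still alive, in hospital and in the study 48 hours later. Mortality and hospital stay are secondary objectives (section 11.2), so the plan itself treats both as things the drug may change. A patient who dies at 20 hours has the worst organ-failure outcome, and one discharged at 40 hours has close to the best. Both leave the primary set, and a new patient takes the place of each.

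A drug that saves the sickest patients keeps high-scoring survivors in its own arm and looks less effective. A drug that hastens death removes them and looks better. Early discharge works the other way: the arm that sends more patients home early loses its lowest scores. Replacement restores the planned numbers per arm without restoring comparability. The result is meant to decide whether a phase 2b study is justified (section 19.1).

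**Working it through.** **Inputs from section 19.1:** difference 2 points, SD 3.43, α 0.05, 70 v 35 pooled and 35 v 35 per dose.

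**Assumptions:** the early death rate q in each arm, and the correlation ρ between risk of early death and latent 48-hour SOFA. The patients at highest risk die. The protocol gives no 48-hour rate. The 35% mortality quoted in section 9.1 has no time point.

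**1. The stated power.** Noncentrality is 2 / (3.43 × √(1/n₁ + 1/n₂)).
- 70 v 35: 2 / (3.43 × 0.2070) = 2.82. A two-sided t-test on 103 df gives 79.7% (stated 80%).
- 35 v 35: 2 / (3.43 × 0.2390) = 2.44. A one-sided t-test on 68 df gives 77.9% (stated 78%).

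Both reproduce. They assume a difference between complete, unselected arms.

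**2. Shift among survivors when the drug has no effect on SOFA.** With z = Φ⁻¹(1−q), removing the top fraction q lowers the survivor mean by ρ × 3.43 × φ(z)/(1−q). At ρ = 1:
- q = 10%: 3.43 × 0.1755/0.90 = 0.669
- q = 15%: 3.43 × 0.2332/0.85 = 0.941
- q = 20%: 3.43 × 0.2800/0.80 = 1.200

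| Early deaths | ρ = 1 | ρ = 0.7 | ρ = 0.5 |
|---|---|---|---|
| 15% v 10% | 0.27 | 0.19 | 0.14 |
| 20% v 10% | 0.53 | 0.37 | 0.27 |

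The shift favours the arm with more deaths and is 7% to 27% of the 2-point target. If that arm is active, the one-sided 5% per-dose test rejects 7% to 11% of the time in the first row and 10% to 20% in the second. Exchanging the rates reverses the sign. Equal rates with no drug effect give no bias.

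**3. A true 2-point effect that also lowers early deaths.** Take 20% on placebo, 10% on active, ρ = 0.7.
- Placebo survivors are lowered by 0.7 × 1.200 = 0.840 and active survivors by 0.7 × 0.669 = 0.468.
- Survivor difference: 2 − (0.840 − 0.468) = 1.63 points.
- Survivor SD is 3.43 × √(1 − ρ²(zλ + λ²)) with λ = φ(z)/(1−q): 3.06 on placebo and 3.18 on active.
- With the arms refilled to 35 and 70, the standard error is √(3.06²/35 + 3.18²/70) = 0.642.
- The ratio is 1.63/0.642 = 2.54 against a critical value of 1.98. Power is about 70%; simulation with replacement also gives 0.70.

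In a second model, death occurs above a fixed latent score and the drug lowers every score by 2. Placebo early deaths of 5%, 10%, 15% and 20% then leave survivor differences of 1.74, 1.58, 1.44 and 1.33 points, with pooled power of 75%, 72%, 68% and 64%.

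**4. Price of ranking deaths worst.** In simulations of 70 v 35 with a 2-point effect, ρ = 0.7 and equal early deaths in both arms, a survivor-only t-test is compared with a rank test that places deaths last, both on the same 105 patients. Power falls from about 81% to 64% at 10% deaths, and from about 82% to 73% at 5%.

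**The case against.** The strongest defence is that this is a phase 2a trial looking for signs of activity in evaluable patients. Section 12.2 excludes patients not expected to survive 48 hours, ITT is also planned, and the separate statistical analysis plan may specify imputation. With equal early death rates and no drug effect there is no bias, and ranking deaths worst then costs power.

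Much of this limits the size of the problem. The exclusion lowers early deaths but cannot remove them, since the replacement rule expects some. ITT is only a comparison. A separate analysis plan could add an imputation rule, but it could not change the primary population or the replacement rule without contradicting the protocol, nor recover data that were not collected.

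Four stronger readings are tempting, and the protocol does not support them.
- **That ITT cannot be computed.** Patients withdrawn after dosing keep safety follow-up, and section 13.8.3 includes platelets, bilirubin, creatinine, blood pressure and GCS. Several SOFA components may therefore survive, although the safety bloods listed there include no later blood gas. The loss is firm only for patients withdrawn before dosing.
- **That the alive component of the 48-hour composite is lost.** Section 19.10 assigns only the primary efficacy analysis to the per-protocol set, and 19.6 names no population for secondary endpoints.
- **That recruitment cannot supply the replacements.** At 15% loss, 105/0.85 means 124 randomised. The loss rate is assumed, however, and section 19.2 gives no enrolment fraction for round-the-clock recruitment.
- **That power collapses because the arms shrink.** The protocol refills them, so the loss in step 3 comes from the smaller survivor difference.

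**Conclusion.** The concern stands. Followed exactly, the protocol makes the primary comparison on a set selected by events after dosing that treatment can change.

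The size is conditional on the assumed death rates and correlation. For early deaths differing by 5 to 10 percentage points, the spurious shift is about 0.14 to 0.53 points, in either direction. For a true 2-point effect with early deaths cut from 20% to 10%, the visible difference is about 1.6 points and pooled power about 70% after replacement. If early deaths are rare, the effect is small. The protocol gives no rate to settle which case applies, and early discharges add a bias that these figures do not count.

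ITT as planned is a weak check. It is secondary, the protocol states no rule for early death or discharge, and section 13.9 may leave it without full SOFA data for withdrawn patients. The two descriptions of the per-protocol set, in 19.10 and 19.12, also disagree on the 48-hour condition. This should be corrected before analysis, because a primary estimate selected in this way cannot be repaired from the selected patients alone.

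**What to change.** - **19.5 and 19.10:** make all randomised patients, as allocated, the main analysis, and keep per protocol as supportive.
- **19.11:** state a value or rank for death before 48 hours that treats it as a worst outcome, and a rule for discharge before 48 hours. Worst rank or a fixed worst score would each serve; the defect does not dictate which.
- **11.6, 13.9 and 19.12:** if extra patients are recruited to offset losses, say that nobody already randomised leaves the analysis.
- **13.9:** keep collecting routine outcome data for every randomised patient, including those found ineligible or deviating, unless consent to data use is withdrawn.
- **19.10 and 19.12:** reconcile the two per-protocol definitions.
- **19.1:** restate the 80% for the chosen analysis.

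The cost is amendment wording and some further data collection, mostly from routine clinical records. The statistical cost is the power shown in step 4: if the drug does not affect early death, ranking deaths worst takes power from about 81% to 64% at 10% early deaths in both arms, or from about 82% to 73% at 5%. That should be weighed openly when the rule is chosen.

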19.6 Secondary outcome analysis

Secondary Outcome Analysis

The secondary endpoints that are continuous variables include: maximum SOFA score, mean SOFA Score (Days 2-5), number of days on organ support, number of ventilation-free days, number of days

in hospital, and number of days in critical care. Placebo and treatment groups will be analysed using appropriate standard tests of two-group comparison depending on data normality.

The secondary endpoints that are catagorical variables include: incidence of acute kidney injury as per the RIFLE classification. Secondary endpoints that are nominal variables include: incidence of prolonged organ failure, incidence of acute lung injury, incidence of infection, mortality rate (28-day, 90-day and discharge), and 'alive and free of multiple organ failure' at 48 hours. Placebo and treatment groups will be analysed using appropriate standard tests of two-group comparison.

19.8 Adjusted analysis

The main analysis will be performed on unadjusted data. Continuous variables will be tested for normality and appropriate tests of comparison will be chosen accordingly.

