The total 60 mls of blood sampled equates to approximately 1% of the total circulating blood volume over the 12-hour period. As recruited patients will be receiving blood transfusions as part of their standard clinical care during this time, it is not anticipated that the samples taken will have any

adverse effects on clinical outcomes. Blood that is collected and not used for PK/PD analysis will be processed and stored for use in ancillary research (See Section 13.3.9)

Clinical Blood Sampling

In order to calculate SOFA and RIFLE scores, ascertain presence of infection, and degree of shock on admission, record will be made the following parameters as part of routine clinical bloods (i.e. no additional specific research blood draws will be taken):

- Platelets
- Creatinine
- Estimated Glomerular Filtration rate (eGFR)
- Bilirubin
- Total white blood cells
- Neutrophils
- Lymphocytes
- C-reactive protein
- Arterial or venous blood gas result (admission result only)

In addition, in order to ensure adequate safety of the IMP, the following will be monitored and for the purposes of safety monitoring for AEs and SAEs:

- Haemoglobin
- Haemocrit
- Red cell count
- Mean cell volume
- Mean corpulscular haemoglobin (MCH)
- Red blood cell distribution width (RDW)
- Mean corpuscular haemoglobin concentration (MCHC)
- White cell count
- Platelet count
- Neutrophils
- Lymphocytes
- Monocytes
- Eosinophils
- Basophils
- Alanine aminotransferase (ALT)
- Aspartate aminotransferase (AST)
- Alkaline phosphate
- Gamma-glutanyl transpeptidase (GGT),
- Bilirubin
- Creatinine
- Urea
- Sodium
- Potassium
- Calcium
- Albumin
- Prothrombin Time
- International Normalised Ratio (INR)

These parameters will be collected daily for days 1-7, and subsequently on day 14±1, day 21±1, and day 27±1, provided the subject is still in hospital. Where possible, these data will be collected from

routine clinical bloods. In the event they have not been undertaken as part of routine clinical bloods, the research fellow will take the bloods at the specified times (unless the subject declines).

Radiological Investigation Results

Radiological investigations (including Chest X-rays and CT scans) undertaken as part of a subjects' clinical course, will be examined for calculation of ARDS scores as well as for assessment of adverse events. No specific radiological investigations will be undertaken for research purposes.

Outcome Measures

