19.0 Statistical and Data Analysis

19.1 Sample size calculation

The primary objective of this trial is to determine the signs of potential efficacy of Artesunate in reducing multiple organ failures and complications. To establish this, the primary comparison of interest will be on the SOFA score at 48 hours.

Each of the Artesunate dose level groups will be compared to placebo. For each dose level the null hypothesis will be that there is no difference in the response rates between Artesunate and placebo, the alternative hypothesis being that the response rate is higher for Artesunate than for placebo.

This is a Phase 2a study and we are looking for safety and efficacy data with which to appropriately power a subsequent definitive 2b trial. A formal sample size calculation is not possible given the lack of existing human efficacy data.

However if Artesunate leads to a clinically relevant 2-point reduction in 48-hour SOFA score, this study will have a power of 80% to detect this difference with 70 intervention and 35 control subjects (α =0.05; σ =3.43) by unpaired t-test.

The intervention arms will consist of 35 subjects receiving Artesunate at 2.4 mg/kg and 35 receiving Artesunate at 4.8 mg/kg. We shall also perform two one-sided t-tests on each of the two intervention arm does levels against the placebo where 35 patients in each arm will detect a 2-point reduction in 48-hour SOFA (α =0.05; σ =3.43) with 78% power.

This should provide enough data on safety profile and potential clinical efficacy to determine whether progression to a 2b study is justified and to develop an appropriate study protocol.

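### The protocol fixes the main 48-hour SOFA analysis as unadjusted, which is valid but gives up precision that a few pre-dose covariates could supply

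*Protocol*

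**What the plan says.** Section 19.8 is titled as the adjusted analysis, but its content is the opposite: "The main analysis will be performed on unadjusted data". It names no covariate and no supplementary adjusted model. Section 19.5 is consistent with it: "placebo and treatment groups will be analysed using standard tests of two-group comparison depending on data normality".

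Section 19.1 powers the trial on the same basis. The target is stated as "if Artesunate leads to a clinically relevant 2-point reduction in 48-hour SOFA score", and the claim is that "this study will have a power of 80% to detect this difference with 70 intervention and 35 control subjects", with "α =0.05; σ =3.43) by unpaired t-test". For each dose against placebo it says "35 patients in each arm will detect a 2-point reduction in 48-hour SOFA", one-sided, with 78% power.

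Section 13.5.1 specifies simple 2:1 randomisation within each stage and names no stratification factor.

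Baseline data are planned in several places. Vital signs, including GCS, are taken at screening (13.8.1, 13.8.3). The routine bloods in 13.8.3, recorded partly to judge shock on admission, include "Arterial or venous blood gas result (admission result only". Section 19.4 summarises "continuous variables (including age, ISS, blood products and fluids in the first 24 hours" by group. That section uses these variables for description and baseline comparability only.

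**The concern.** The choice is written into the protocol. A SAP that made an adjusted model primary would contradict section 19.8, so this is not a detail left for later.

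The design is one in which adjustment tends to help. The arms have 35 patients, allocation is simple, and the background (9.1) itself says that organ failure rises with blood loss and shock. If severity differs between arms by chance, an unadjusted test does not correct for it. If severity predicts SOFA, the unadjusted test also carries variance that could have been removed. What is at stake is the width of the interval for the main efficacy estimate, which section 19.1 intends to use in deciding on and designing a phase 2b trial.

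**Working it through.** **Inputs from section 19.1.** Difference 2 points; SD 3.43; α 0.05; 70 v 35 (two-sided reproduces the stated figure) and 35 v 35 (one-sided, as stated).

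**Step 1: reproduce the stated power.** Noncentral t with SE = 3.43·√(1/n₁ + 1/n₂), noncentrality 2/SE and N − 2 degrees of freedom.
- 70 v 35: SE = 0.710, noncentrality 2.82, 103 df, power 79.7% (stated 80%).
- 35 v 35: SE = 0.820, noncentrality 2.44, 68 df, power 77.9% (stated 78%).

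Both stated figures are right for the unadjusted test.

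**Step 2: adjust, and pay for it.** With k pre-dose covariates that jointly explain a share R² of the variance, the residual variance is 3.43²·(1 − R²). Estimating the covariates and allowing for their random imbalance inflates the variance of the treatment effect by about (N − 3)/(N − k − 3), and the degrees of freedom fall to N − 2 − k.
- N = 105: 102/99 = 1.030 for k = 3; 102/97 = 1.052 for k = 5.
- N = 70: 67/64 = 1.047 for k = 3; 67/62 = 1.081 for k = 5.

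The documents give no R², so a range is shown. The first figure in each pair is for k = 3 and the second for k = 5.

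| Assumed R² | 70 v 35 SE | 70 v 35 power, two-sided | 35 v 35 SE | 35 v 35 power, one-sided |
|---|---|---|---|---|
| Unadjusted | 0.710 | 79.7% | 0.820 | 77.9% |
| 0 | 0.721, 0.728 | 78.5%, 77.6% | 0.839, 0.852 | 76.3%, 75.1% |
| 0.1 | 0.684, 0.691 | 82.6%, 81.8% | 0.796, 0.809 | 80.0%, 78.9% |
| 0.2 | 0.645, 0.651 | 86.7%, 86.0% | 0.750, 0.762 | 84.0%, 82.9% |
| 0.3 | 0.603, 0.609 | 90.7%, 90.2% | 0.702, 0.713 | 88.0%, 87.1% |

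**Step 3: break-even.** Setting (1 − R²)(N − 3)/(N − k − 3) = 1 gives R² = k/(N − 3). For N = 105 this is 3/102 = 0.03 to 5/102 = 0.05. For N = 70 it is 3/67 = 0.045 to 5/67 = 0.075.

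**Step 4: chance imbalance.** For one baseline factor, the chance that the arms differ by more than 0.3 SD is 2·[1 − Φ(0.3/√(1/n₁ + 1/n₂))]: about 21% at 35 v 35 and 15% at 70 v 35. If that factor explains 20% of SOFA variance, a 0.3 SD imbalance moves the SOFA difference by 0.3 × √0.2 × 3.43 = 0.46 points, against a target of 2.

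**Step 5: which variables qualify.** Only pre-dose values do.
- SOFA is first scored in the 0-12 hour window after dosing (13.8.1), so there is no baseline SOFA.
- Blood products and fluids over the first 24 hours run largely after dosing, which is due within 2 hours of admission (15.13).
- The blood gas is placed inconsistently. Section 13.8.3 calls it the admission result, whereas 13.8.1 lists a baseline arterial gas among the procedures after dosing.
- The CRF element list in 20.7 names neither injury severity score nor blood gas.

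**The case against.** The strongest reply is that nothing here is stated wrongly. Randomisation makes the unadjusted comparison valid, and the power claim matches the planned test and is correct. This is a phase 2a trial meant to inform a later one, and the word main leaves room for a supplementary adjusted analysis. All of that stands. A reader might infer that the main analysis is biased, that its type I error is inflated, or that 80% is overstated. The documents support none of these: chance imbalance is already part of the unadjusted standard error.

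The size of the gain is also open to challenge. R² is assumed, and eligibility may lower it. Entry needs systolic pressure below 90 with minimal response to fluid (12.1), and GCS 3 at scene is excluded (12.2), so shock and GCS have a restricted range. Sedation and ventilation (13.3.6) may make GCS a noisy predictor. Taking only √(1 − R²) off the SD would suggest 84%, 88% and 92% for 70 v 35 at R² 0.1, 0.2 and 0.3, which ignores the price of estimating the covariates. The table above charges it.

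A reader might also take per-dose power as about 62%, from 35 v 17. That is not the planned comparison: section 19.1 sets each dose against all 35 placebo patients. Which placebo patients to use is a separate question.

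Finally, section 19.4 lists 24-hour products and fluids beside baseline variables, and a reader might infer that the plan would adjust for them. It only summarises them. This is a labelling point and a caution for whoever writes the model.

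**Conclusion.** The point holds as a recommendation on efficiency. The main analysis is fixed as unadjusted in a small trial with simple randomisation that already intends to record plausible predictors before dosing. The test is valid and its power is correctly stated; the loss is in precision and in protection against chance imbalance.

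Allowing for three to five covariates, pooled power would rise from about 80% to 82-83%, 86-87% or 90-91% at R² 0.1, 0.2 or 0.3. Per-dose power would rise from 78% to 79-80%, 83-84% or 87-88%. If the covariates explain nothing, power falls by about 1-2 points (pooled) or up to about 3 points (per dose). The gain is therefore modest at R² 0.1 and worthwhile from about 0.2.

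These figures assume a linear model, the protocol's SD of 3.43 and an R² that the documents do not supply. The per-dose figures also assume the planned 35 v 35 comparison without a stage term.

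**What to change.** Amend 19.8, and 19.5 to match. The main analysis becomes a linear model of 48-hour SOFA on treatment, with stage and two or three named pre-dose covariates: for example age, injury severity score, and either an admission blood-gas shock marker or screening GCS. Keep the unadjusted two-group test as a sensitivity analysis. Keep the list short, because each covariate costs most in the dose-level comparisons.

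Decide separately whether stage enters the dose-level models. Each dose is given in one stage only, so a stage term would leave each dose compared with its own 17 or 18 placebo patients instead of all 35.

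Before naming the covariates:
- confirm that each is captured on the CRF (20.7);
- reconcile 13.8.1 with 13.8.3, so that the blood gas used is the admission sample taken before dosing;
- state that post-dose SOFA and 24-hour products and fluids are not covariates, and label the latter in 19.4 as recorded after dosing.

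The cost is a few sentences in the protocol and SAP, possibly one or two CRF fields, a simple rule for missing baseline values, and the small loss of power if the covariates prove barely prognostic. No extra patients are needed.
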